### **Immediate analysis for surveillance purposes**

The incidence of both neonatal COVID-19 and the incidence of babies born to mothers with COVID-19 infection that require neonatal care will be estimated cumulatively each month using an estimate of the monthly births and maternities respectively. Case fatality will also be estimated as deaths as a proportion of all confirmed cases. The proportion of COVID-19 associated neonatal admissions will be estimated using an estimate of the admissions to neonatal units. In the absence of concurrent national data, the denominators will be estimated from monthly totals of births and maternities in 2019 using data from the national MBRRACE-UK surveillance programme, and from total monthly neonatal unit admissions in 2019 using data from the National Neonatal Research Database. We will ensure that we use corresponding months from 2019 data to account for seasonal variations in both births and neonatal unit admissions.

We will also use data collected from the UKOSS study to identify cases due to vertical transmission.

Each incoming case will be reviewed by the investigator team, on a weekly basis in order to identify early signals from the surveillance of recurring patterns in presentation. For example, we may find all infections are nosocomial and would therefore examine characteristics of, for example, infections associated with particular modes of respiratory such as non-invasive ventilation. This information, together with the cumulative incidence and case fatality, will be fed through to PHE, PHS, PHW and PHNI, DHSC, NHSE, the devolved governments, and the Royal Colleges of Obstetricians and Gynaecologists and Paediatrics and Child Health and the British Association of Perinatal Medicine, and organisations responsible for ensuring that the care provided meets the needs of mothers and babies (for example CQC in England) to ensure that the information is immediately available to support policy and clinical decision-making.

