### 3. SYNOPSIS

It may be useful to include a brief synopsis of the study for quick reference and/or to use as a standalone document. Complete information and, if required, add additional rows.

|                                 |   |   |   |
|---------------------------------|---|---|---|
| Study Title                     | Neonatal Complications of Coronavirus Disease (COVID-19) Study  |   |   |
| Internal ref. no. / short title | Neonatal complications of COVID-19  |   |   |
| Study registration              | Not applicable   |   |   |
| Sponsor                         | University of Oxford
Clinical Trials and Research Governance (CTRG)
Joint Research Office,
[name],
[name],
[name]  |   |   |
| Funder                          | Department of Health and Social Care, through the Policy Research Programme, as a grant to the NIHR Policy Research Unit in Maternal and Neonatal Health and Care, based at the NPEU.   |   |   |
| Study Design                    | National observational study  |   |   |
| Study Participants              | Any baby: 
 
1. That has a diagnosis of COVID-19 made on a sample taken before 29 days of age and receives inpatient care for COVID-19 (this includes postnatal ward, neonatal unit, paediatric inpatient wards, paediatric intensive care unit (PICU))
 
 
OR
 
 
2. Where the mother had confirmed COVID-19 at the time of birth or suspected COVID-19 at the time of birth that has subsequently been confirmed, and the baby was admitted for neonatal care
 
 |   |   |
| Sample Size                     | Uncertain at this stage – too little information available to be able to estimate   |   |   |
| Planned Study Period            | 13 months surveillance with 6 months follow-up to ensure ascertainment of all outcomes.   |   |   |
| Planned Recruitment period      | Start: As soon as all permissions are in place – 1st April 2020
End: 13 months after the start date – 31st April 2021  |   |   |
|                                 | Objectives  | Outcome Measures  | Timepoint(s)  |
| Primary (1)                     | To estimate the incidence of neonatal COVID-19 including  | Incidence of confirmed SARS-CoV-2 in neonates that receive inpatient care | Collected during admission or after discharge/death |

|                 |   |   |   |

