## 5. BACKGROUND AND RATIONALE

### Background

The novel coronavirus SARS-CoV-2 is pandemic and is increasingly being detected in the United Kingdom. The virus leads to coronavirus disease (COVID-19) in a proportion of infected patients with a higher risk of severe disease and mortality in older adults and those with co-morbidities. We expect a rapid increase in cases of COVID-19, a situation described as “the worst public health crisis for a generation” by the United Kingdom government, which has raised the national risk level to high.

To date there is only limited data describing the incidence, clinical course, treatments and outcomes of COVID-19 in newborn babies and children. A retrospective review of 1,099 cases of COVID-19 in China (14.2% of identified national cases at the end of January 2020) identified only 9 children (Guan et al., NEJM 2020). A retrospective study of 266 hospitalised children in Wuhan, China isolated the virus in only six children (range 1-7 years age), and only one child had severe disease requiring intensive care (Liu et al., NEJM 2020). Three cases of neonatal COVID-19 have been described (Lu et al., J Med Virol 2020), with the first case reported in the UK on 13th March, and as of 20th March two cases in total are known in the UK.

Transmission of neonatal COVID-19 appears to occur mainly in family clusters and a retrospective review of nine pregnant women with COVID-19 pneumonia in China found no evidence of vertical transmission (Chen et al., Lancet 2020). However, the recent UK cases raise the concern that vertical transmission is a potential issue as both mother and baby are infected in at least one of the UK cases. The virus is known to be contained within most bodily secretions and there are suggestions that faecal oral transmission occurs, raising the possibility of transmission from mother to baby at birth even if not prenatally.

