#### **11.5. Decision points**

We will look at the data on a weekly basis. Advice will be provided to DHSC, PHE, NHSE, Welsh, Scottish and Northern Irish Governments. The study will continue.

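### The surveillance incidence sent out for immediate decisions is a running cumulative rate, which responds less to a change in current incidence each month; a monthly rate should be reported beside it

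*Protocol*

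**What the plan says.** Protocol section 7, under Immediate analysis for surveillance purposes, defines two incidences: neonatal COVID-19, and babies of infected mothers who need neonatal care. Both "will be estimated cumulatively each month using an estimate of the monthly births and maternities respectively". The denominators come from 2019 births and maternities, matched by calendar month: "We will ensure that we use corresponding months from 2019 data to account for seasonal variations".

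The same subsection says what is sent out. After describing the weekly case review it continues: "This information, together with the cumulative incidence and case fatality, will be fed through to PHE" and a list of other bodies, "to ensure that the information is immediately available to support policy and clinical decision-making".

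Three other places bear on the point. The Background in section 5 says "We expect a rapid increase in cases of COVID-19". The Synopsis plans "13 months surveillance with 6 months follow-up to ensure ascertainment of all outcomes". The weekly review in section 7 is done "in order to identify early signals from the surveillance of recurring patterns in presentation", and section 11.5 adds "We will look at the data on a weekly basis". The protocol names no monthly, rolling or other period-specific incidence.

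**The concern.** A cumulative rate averages over everything since the start. That suits the question of how common the condition was over the whole study. It does not suit the question a policy body asks in a given month, which is how common the condition is now and whether it is going up or down. The longer surveillance runs, the more past months are in the average and the less the newest month counts.

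The protocol expects rapid change, accumulates for up to 13 months, and gives the cumulative figure to people making immediate decisions. A real rise or fall late in the study would then reach them in much weakened form. The weekly review does not fill the gap as written, because it concerns patterns in how individual cases present, and the weekly look in section 11.5 names no rate.

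**Working it through.** The protocol gives no expected incidence or case number (section 11.3 says none can be estimated), so there is no planned figure to reproduce. The check is on how the chosen measure behaves.

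**Inputs from the protocol.** Cumulative estimate updated monthly, with month-matched denominators (section 7); accumulation for up to 13 months (Synopsis and section 9.11).

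**Assumptions.** Equal monthly births, and several hypothetical paths of relative monthly incidence. None of these paths is in the documents.

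**Formula.** Let r_k be the rate in month k and C_k the cumulative rate after month k. With equal denominators

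C_k = [(k − 1) × C_(k−1) + r_k] / k = C_(k−1) + (r_k − C_(k−1)) / k.

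The figure moves by one k-th of the gap between the current rate and the past average.

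**Stable incidence, then a change in month k.** Set the earlier rate to 1, so C_(k−1) = 1.

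| Month k | Doubling: rise of 1/k | Tripling: rise of 2/k |
|---|---|---|
| 6 | 1/6 = 17% | 2/6 = 33% |
| 10 | 1/10 = 10% | 2/10 = 20% |
| 13 | 1/13 = 8% | 2/13 = 15% |

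The true changes are +100% and +200%. No earlier peak is needed for this damping.

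**A sustained change.** Rate 1 for six months, then 3 for months 7 to 13: C_13 = (6 × 1 + 7 × 3) / 13 = 27/13 = 2.08. Seven months after the rise, the reported figure is still about two thirds of the current rate of 3.

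**If there was an earlier peak (assumption).**
- Rates 10, 4, 1, 1, 1, 1, then 3: C_6 = 18/6 = 3.0 and C_7 = 21/7 = 3.0. The figure is flat while the monthly rate triples.
- Rates 3, 6, 3, 1, 1, 1, then 1.5, 2, 3: C_6 = 15/6 = 2.50 and C_9 = 21.5/9 = 2.39. The figure ends lower while the monthly rate triples between months 6 and 9.

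By the formula, the figure is exactly flat when r_k = C_(k−1). A tripling is therefore hidden completely only if the preceding month stood at one third of the running average.

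**Is the monthly rate available?** Yes. The denominators are already assembled by calendar month. With unequal monthly denominators of 0.92 to 1.03 times a base value, differencing successive cumulative totals returned the assumed monthly rates exactly.

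**The case against.** The strongest reply has five parts.

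**The analysis plan may add a monthly rate.** Section 11.2 refers to a statistical analysis plan that is not at hand, and the protocol does not forbid other measures. So a reader might infer that the cumulative rate is the only incidence that will ever be produced, but the documents do not say so. What stands against this reply is that section 7 itself chooses the measure and names it as the one sent out. That is a stated choice, not a detail left open.

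**Waves are not in the documents.** The protocol expects a rapid increase and no more. It is tempting to say that the disease comes in waves and that the figure will therefore stay flat through a resurgence, but the text does not support that. In a purely rising epidemic the cumulative rate rises too, though late. The supported result is damping; flatness is a special case.

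**The cumulative figure is right for the primary objective.** Section 6 asks for incidence over the study, and a cumulative estimate answers that. A reader might conclude that the final 13-month estimate is at fault. The quoted text is about the immediate analysis and does not say how the final result will be presented, so this does not follow.

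**Nothing is lost, and recipients have other signals.** Cases are notified weekly and reviewed weekly, and anyone holding successive counts and denominators can take differences. This is true, and it makes the matter one of reporting, not bias. But section 7 promises recipients the cumulative incidence, not the components, and they should not have to rebuild the current rate.

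**Monthly counts may be very small.** Section 5 knew of two UK cases by 20 March 2020. If 1 and then 3 were actual counts, equal rates would put at least 3 of the 4 in the later month with probability (4 + 1)/16 = 31%. This stands. It calls for intervals and for pooling of sparse months; it is no reason to omit a period-specific rate.

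**Conclusion.** The point holds as a cheap improvement to the surveillance output. The protocol fixes a cumulative rate as the incidence reported for immediate decisions, and by construction that rate responds less to current change the longer the study runs. After stable incidence, a one-month doubling shows as +17% at month 6 and +8% at month 13, and a tripling as +33% and +15%. These figures rest on equal monthly births and a stable rate beforehand. A flat or falling figure during a rise needs the further assumption of an earlier peak.

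The finding is confined to the real-time use of the figure. The cumulative rate is a valid whole-period estimate, and the point is no criticism of the primary objective.

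**What to change.** In section 7, amend the sentence so that both incidences are estimated for each calendar month (pooled over two or three months where counts are very small) and cumulatively, with 95% confidence intervals. Send both figures to the listed bodies, with recent months marked provisional.

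State one rule for assigning cases to months that matches numerator to denominator. This matters because section 8.2 admits samples taken up to 28 days of age, so a baby can be born in one month and test positive in the next. Two rules would work:
- month of birth for all cases, with the latest month marked incomplete until its babies have passed 28 days; or
- month of first positive sample for infected babies, with that month's births described as an approximation to the neonates at risk. Babies included only because of the mother's infection may have no positive sample and would stay with month of birth.

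Section 16.7 converts event dates to days and weeks before transfer for analysis, so the calendar month should be derived and kept before that step.

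The cost is a wording change. Month-matched denominators are already planned and the dates are collected. The downside is imprecise monthly rates and revision of recent months as late forms arrive, which the intervals, the pooling and the provisional label make visible.

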## **8. PARTICIPANT IDENTIFICATION**

### **8.1. Study Participants**

All neonates in the United Kingdom receiving care in hospital who are infected with COVID-19 and all newborn babies receiving care in a neonatal unit following birth to mothers infected with COVID-19.

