### **8.2. Inclusion Criteria**

Any baby:

1. That has a diagnosis of COVID-19 made on a sample taken before 29 days of age and receives inpatient care for COVID-19 (this includes postnatal ward, neonatal unit, paediatric inpatient wards, PICU)

OR

2. Where the mother had confirmed COVID-19 at the time of birth or suspected COVID-19 at the time of birth that has subsequently been confirmed, and the baby was admitted for neonatal care

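### One monthly surveillance rate counts babies but divides by maternities, so it is neither a proportion of births nor a proportion of maternities; the effect is small

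*Protocol*

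**What the plan says.** The protocol names its population denominators in one place: Section 7, under the heading on immediate analysis for surveillance. Four measures are set there.

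- **Neonatal COVID-19 incidence**, over births.
- **Exposed-baby incidence**, that is "the incidence of babies born to mothers with COVID-19 infection that require neonatal care". This and the first measure "will be estimated cumulatively each month using an estimate of the monthly births and maternities respectively", so the second takes maternities.
- **Case fatality**, deaths over confirmed cases.
- **Admissions proportion**: "The proportion of COVID-19 associated neonatal admissions will be estimated using an estimate of the admissions to neonatal units". The denominator comes "from total monthly neonatal unit admissions in 2019 using data from the National Neonatal Research Database".

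On sources, the text says: "In the absence of concurrent national data, the denominators will be estimated from monthly totals of births and maternities in 2019". Corresponding calendar months of 2019 are used to allow for season.

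The case definition (Section 8.2) has two limbs. The first covers infected babies in several inpatient settings ("this includes postnatal ward, neonatal unit, paediatric inpatient wards, PICU"). The second covers babies of infected mothers, with the condition "and the baby was admitted for neonatal care". Section 8.1 describes this second group as "all newborn babies receiving care in a neonatal unit following birth to mothers infected with COVID-19".

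The identifier table in Section 7 includes the mother's NHS/CHI/HSCN number, collected for linkage.

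**The concern.** A rate is easy to interpret when each unit in the numerator is also a unit in the denominator. In the exposed-baby incidence it is not. The numerator unit is a baby needing neonatal care; the denominator unit is a maternity, which may produce more than one baby. What results is a count of babies per maternity. It cannot be read as the chance that a newborn is affected, nor as the chance that a maternity is affected.

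The two incidences reported side by side each month also have different bases, one per birth and one per maternity, so they cannot be compared or added without conversion. Section 7 sends the cumulative incidence to public health bodies, governments and professional colleges for immediate use. Readers there are likely to take the figure as a plain proportion.

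**Working it through.** The protocol states no value for this rate, so there is no figure to reproduce. The check compares the units of each measure and then sizes the one mismatch.

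**Units**

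| Measure | Numerator | Denominator | Units agree? |
|---|---|---|---|
| Neonatal COVID-19 | babies | births | yes |
| Babies of infected mothers needing neonatal care | babies | maternities | no |
| Case fatality | deaths among cases | confirmed cases | yes |
| Admissions proportion | COVID-19-associated neonatal admissions, not defined further | neonatal-unit admissions | yes, if the numerator means neonatal-unit admissions |

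**Notation.** A = admitted babies of infected mothers; K = mothers with at least one such baby; B = all births; M = all maternities. The plan computes A/M.

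**Comparison 1: babies over births, A/B.** The numerator is unchanged, so the plan's figure is too high by (A/M)/(A/B) = B/M. If a share m of maternities are twin maternities and the rest singleton, B/M = 1 + m. The protocol does not give m, so 1-2% is assumed.

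- m = 0.01: 1.01
- m = 0.015: 1.015
- m = 0.02: 1.02

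The proportion of multiples among admitted babies does not enter this comparison.

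**Comparison 2: affected mothers over maternities, K/M.** The denominator is unchanged, so the plan's figure is too high by A/K. If a share s of admitted babies are twins and both of each pair are admitted, each pair has one mother, so K = A × [(1 - s) + s/2] and A/K = 1/[(1 - s) + s/2]. The protocol does not give s, so values are assumed.

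- s = 0.05: 1/0.975 = 1.03
- s = 0.10: 1/0.950 = 1.05
- s = 0.20: 1/0.900 = 1.11
- s = 0.25: 1/0.875 = 1.14
- s = 0.30: 1/0.850 = 1.18

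Where only one twin is admitted, that baby counts once and so does the mother. The factor for a given s is then lower, falling to 1.00 if no pair has both admitted.

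The two comparisons answer different questions. Comparison 1 gives the error if the intended quantity is the proportion of births; comparison 2 gives it if the intended quantity is the proportion of maternities.

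**Admissions proportion, conditional only.** If the numerator is limited to neonatal-unit admissions, the factor is 1.00. If cases from every eligible setting were counted, and a share f of them never entered a neonatal unit, the overstatement would be 1/(1 - f): 1.11 at f = 10% and 1.33 at f = 25% (assumed values). The text does not say that such cases are counted.

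**The case against.** The strongest defence is one of scale and place. Against the simplest remedy, a births denominator, the discrepancy is only 1-2% under the assumption above. The larger 5-14% belongs to a different target quantity and requires both twins to be admitted. The rate is an interim monthly figure that does not appear among the primary or secondary outcomes in Section 6. The incidence of neonatal COVID-19 has matching units here, and nothing shows that the vertical-transmission outcome uses the mismatched ratio. All of this stands, and it limits the weight of the point. It does not remove it, because the pairing is stated in the text and not left open for the statistical analysis plan.

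A reader might infer several stronger points that the protocol does not support.

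- **Cases on any ward are divided by neonatal-unit admissions.** Section 7 never says this. Its wording can naturally be read as neonatal-unit admissions above and below the line, and Section 8.1 places the maternal-exposure babies in a neonatal unit. The wider list of settings belongs to eligibility. At most the numerator is not spelled out, which the statistical analysis plan may do.
- **Using 2019 totals is an error.** They are used expressly because concurrent data are lacking, for immediate reporting, and matched by month. If an actual denominator were 5-15% below its 2019 value (assumed), the rate using it would be understated by 5-15%, since the reported-to-true ratio is 1 - x for a fall of x. Whether final rates are recomputed can be left to the analysis plan.
- **A change in admissions would distort every rate.** Only the admissions proportion uses admissions. The two incidences use births and maternities, and case fatality uses confirmed cases.
- **Intervals are too narrow because twins are treated as independent.** The protocol specifies no interval for these rates, so there is no stated method to criticise.

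**Conclusion.** The point holds for one of the four surveillance measures. The incidence of babies of infected mothers who require neonatal care divides babies by maternities, and the text leaves no other reading. The result is a ratio of babies per maternity and not a proportion of either unit.

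The numerical effect is small: about 1-2% against births, assuming 1-2% of maternities are multiple, or about 5-14% against affected mothers per maternity, assuming 10-25% of admitted babies are twins with both admitted. The direction is the same in both cases: the stated rate is too high. Neither range comes from the protocol.

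This is a minor correction to an interim figure. It casts no doubt on the neonatal COVID-19 incidence or on case fatality. The definition of the admissions proportion and the status of the 2019-based rates could be made clearer, but neither is shown to be wrong.

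**What to change.** Amend the sentence in Section 7 in one of two ways:

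1. Use births as the denominator for both incidences. The births total is already obtained for the first, so nothing new is needed, and the two rates then share a base.
2. Keep maternities, and count mothers with at least one baby admitted for neonatal care. The maternal NHS/CHI/HSCN number already collected allows siblings to be grouped.

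Name the resulting rate after its unit, per birth or per maternity.

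Two optional clarifications fit in the same paragraph: that the admissions proportion counts only cases admitted to a neonatal unit, and that rates based on 2019 totals are provisional until observed totals are available.

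The cost is a wording change and a rerun of simple ratios. No new data collection is required.

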**6. OBJECTIVES AND OUTCOME MEASURES**

|             | Objectives  | Outcome Measures   | Timepoint(s)                                 |
|-------------|--|---|---|
| Primary (1) | To estimate the incidence of neonatal COVID-19 including nosocomial transmission | Incidence of confirmed SARS-CoV-2 in neonates that receive inpatient care   | Collected during admission or after discharge/death |
| Primary (2) | To estimate the incidence of vertically transmitted COVID-19                     | Incidence of confirmed neonatal SARS-CoV-2 from a sample taken within 12 hours of birth in neonates born to a positive mother | Collected during admission or after discharge/death |

|                        |   |  |   |
|------------------------|---|--|---|
| Secondary (1)          | To describe the clinical presentation natural history and clinical presentation of neonatal COVID-19 and of nosocomial COVID-19 | Clinical signs at presentation: respiratory rate, requirement for ventilation, temperature, other system involvement, multi-organ failure                      | Collected during admission or after discharge/death |
| Secondary (2)          | To describe the clinical presentation of neonates whose mothers are COVID-19 positive   | Clinical signs at presentation: respiratory rate, requirement for ventilation, temperature, other system involvement, multi-organ failure , and investigations | Collected during admission or after discharge/death |
| Secondary (3)          | To describe the outcomes for neonates with COVID-19   | Outcomes: complication as a consequence of COVID-19 e.g. chronic lung disease (y/n); discharge home (y/n); death (y/n); transfer (y/n); still admitted (y/n)   | Collected during admission or after discharge/death |
| Secondary (4)          | To describe the clinical treatments being used to manage neonatal with COVID-19   | Management: respiratory support, cardiovascular support, treatment of fever and other complications; antiviral and other COVID-19 specific treatments used     | Collected during admission or after discharge/death |
| Secondary (5)          | To describe the neonatal secondary impacts of maternal management for COVID-19  | Pre-term birth and reason, delayed resuscitation; Apgar scores, receipt of therapeutic hypothermia, mode of birth  | Collected during admission or after discharge/death |
| Exploratory objectives | Not applicable   |  |   |

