### Data collection

The BPSU will include neonatal complications of COVID-19 on the surveillance card that is sent routinely to all paediatricians and neonatologist in the UK. The surveillance cards will be sent out on a weekly basis. The reporters will notify cases to the BPSU who will forward the notifications to the research team. The research team will then send the study-specific data collection form to the notifying doctor.

The data collected will include identifiers to: (i) cross-checking with other sources of data to ensure complete case ascertainment; (ii) de-duplication; (iii) later linkage to collect further treatment details and outcomes.

The identifier swill comprise:

| Identifier             | Justification  |
|------------------------|--|
| For the baby:   |  |
| NHS/CHI/HSCN Number    | De-duplication and linkage                                       |
| Date of Birth          | Calculation of age at various events, de-duplication and linkage |
| Sex                    | As a clinical descriptor, de-duplication and linkage             |
| Partial Postcode       | To map the regional burden of disease                            |
| Ethnicity              | As a clinical descriptor   |
| Baby date of death     | Calculation of age at death, age-specific risk of death, linkage |
| For the mother: |  |
| NHS/CHI/HSCN number    | Linkage  |

The clinical information collected will comprise: additional demographic descriptors, clinical descriptors, clinical management information and the outcome.

Where the outcome information is not known at the time of data return, the doctor will be re-contacted to collect this data later when this information is likely to be known.

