### **9.10. Early Discontinuation/Withdrawal of Participants**

Early discontinuation is not relevant.

Parents can chose to withdraw the information about their baby from the study. The fact that the infant was infected with COVID-19 or born to a mother with COVID-19 will be retained in the dataset to ensure that incidence rates are based on complete data. The additional identifiable and clinical and demographic data will be deleted from the dataset if parents request to opt-out their baby from the study. In Northern Ireland parents will be approached for consent and may chose not to participate in the study. They will also be able to opt-out later should they change their mind about participating.

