#### **11.8. Procedure for Accounting for Missing, Unused, and Spurious Data.**

Data about all cases will be used even where some data items are missing.

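### Interim case fatality divides deaths so far by all confirmed cases, with unresolved babies counted as non-deaths; it tends to understate eventual fatality and goes out with no bounds or count of open outcomes

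*Protocol*

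**What the plan says.** Protocol section 7, under Immediate analysis for surveillance purposes, defines the estimator: "Case fatality will also be estimated as deaths as a proportion of all confirmed cases". The preceding sentence says that the incidences "will be estimated cumulatively each month using an estimate of the monthly births and maternities respectively". Case fatality follows with the word 'also', so a cumulative monthly calculation is the natural reading, although the interval is stated only for incidence. On use, the same section says: "This information, together with the cumulative incidence and case fatality, will be fed through to PHE" and a list of other public bodies, governments and Royal Colleges, "to ensure that the information is immediately available to support policy and clinical decision-making".

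The protocol expects outcomes to be open when a form comes in. Section 6 lists the outcome categories as "discharge home (y/n); death (y/n); transfer (y/n); still admitted (y/n". Section 7, Data collection, adds: "Where the outcome information is not known at the time of data return, the doctor will be re-contacted to collect this data later". Section 9.11 allows six months of follow-up data collection after 13 months of case identification.

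Two further rules bear on the ratio. Section 11.8 says: "Data about all cases will be used even where some data items are missing". Section 9.10 keeps the fact that an opted-out baby was infected, for the sake of complete incidence rates, but: "The additional identifiable and clinical and demographic data will be deleted from the dataset if parents request to opt-out their baby from the study".

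**The concern.** A confirmed case can enter the denominator as soon as it is notified. A death can enter the numerator only after it has happened and been recorded. In a cumulative ratio taken while cases are accruing, every baby with an open outcome contributes to the denominator alone. The younger the caseload, the larger that group, and the Background (section 5) expects cases to increase rapidly.

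Two consequences follow. Recipients may take an immature figure as the risk of death in infected newborns. The ratio will also tend to climb as outcomes mature, even if lethality is unchanged, and that climb could be read as worsening disease. Nothing in the protocol lags the figure, bounds it, or requires the number of open outcomes to be shown beside it. The formula and its immediate release are fixed in the protocol itself, so this is not a detail left to the statistical analysis plan.

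**Working it through.** The protocol states no case fatality figure, so there is none to reproduce. The check is how far the stated estimator falls short of the eventual fatality of the confirmed cases.

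**Inputs from the protocol:** the estimator (section 7); 13 months of case identification and six months of follow-up (section 9.11); expected rapid growth (section 5).

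**Assumptions, not in the protocol:** the delay from confirmation to recorded death is exponential with mean m = 7, 14 or 28 days; cases enter the count at once, except in step 4; the growth scenario doubles every 14 days, so r = ln 2 / 14 = 0.0495 per day.

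**1. Steady incidence, day T = 30.** Ratio of interim to eventual fatality = 1 − (m/T)(1 − e^(−T/m)).
- m = 7: 0.77
- m = 14: 0.59
- m = 28: 0.39

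At T = 90 the same formula gives 0.92, 0.84 and 0.70.

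**2. Growth starting at day 0, day T = 30.** Ratio = 1 − r(e^(rT) − e^(−T/m)) / [(r + 1/m)(e^(rT) − 1)], with e^(rT) = 4.416.
- m = 7: 0.67
- m = 14: 0.48
- m = 28: 0.31

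Each value is below its steady-incidence counterpart at day 30, so growth makes the shortfall worse.

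**3. Growth sustained for a long time.** Ratio = 1/(1 + rm).
- m = 7: 1/1.347 = 0.74
- m = 14: 1/1.693 = 0.59
- m = 28: 1/2.386 = 0.42

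These are limiting values and should not be set beside the day-30 figures in step 1.

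**4. Cases also enter late, with exponential mean delay c, under sustained growth.** Ratio = (1 + rc)/(1 + rm).
- m = 14, c = 0: 0.59
- m = 14, c = 7: 1.347/1.693 = 0.80
- m = 14, c = 14: 1.00
- m = 7, c = 14: 1.693/1.347 = 1.26

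The sign depends on which delay is longer.

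**5. After follow-up.** Take 395 days of steady incidence and then 180 days with no new cases. Ratio = 1 − (m/395)(e^(−180/m) − e^(−575/m)), which is 1.0000 for m = 7 and 14, and 0.9999 for m = 28.

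**6. What an interim report could show.** Take a hypothetical 60 confirmed cases: 2 deaths, 28 discharged alive, 30 unresolved.
- Protocol formula: 2/60 = 3.3%. This is the lowest value possible for these 60 babies.
- All unresolved babies die: (2 + 30)/60 = 53.3%. This is the true upper bound.
- Deaths among resolved cases: 2/(2 + 28) = 6.7%. This is not a bound.

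Resolved-only fatality can err either way. With a true value of 3% and sustained 14-day doubling:
- Mean 14 days to death and 7 to discharge: 0.03/1.693 = 0.0177 and 0.97/1.347 = 0.7203, giving 0.0177/(0.0177 + 0.7203) = 2.4%, below the truth.
- Mean 7 days to death and 28 to discharge: 0.0223/(0.0223 + 0.4065) = 5.2%, above it.

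**The case against.** The strongest objection is that cases are delayed as well as deaths. Reporting runs through weekly cards and then a form, with a reminder after one week and a telephone call after a second. Deaths have another route in through MBRRACE-UK. Step 4 shows that equal delays remove the bias and that faster recording of deaths reverses it. This stands: a reader might infer that the interim figure is certainly too low, but the protocol gives neither delay, so direction and size are conditional. Even so, no source can count a death that has not yet happened, and for the babies in a given report the ratio can only rise as their outcomes close.

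A second objection is that case fatality is not a primary outcome and that the figure repairs itself through re-contact and six months of follow-up. This also stands. A reader might infer that the study's final case fatality is biased; step 5 does not support that.

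Third, the protocol never calls open cases survivors, and section 11.8 is a general rule on incomplete records that does not set a missing outcome to alive. That is correct. The effect comes from the arithmetic of the ratio, not from a stated imputation.

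Fourth, section 9.10 keeps opted-out cases for incidence and does not say how case fatality treats them. No opt-out numbers are given, so this is a secondary matter of unknown and possibly small size.

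**Conclusion.** The point holds for the interim figure. As written, the estimator puts unresolved babies in the denominator as non-deaths, and the result is released for immediate use without bounds. It tends to understate the eventual fatality, provided deaths are recorded later than cases enter the count, and more so while cases are rising. Under the assumed delays with no case-entry delay, a day-30 report would show between about a third and three quarters of the eventual value (0.31 to 0.77 across steady and growing incidence). A reader might take the long-run growth range of 0.74 to 0.42 as applying at any time; it does not, because growth that starts at day 0 gives 0.67 to 0.31 at day 30.

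The definitive figure after follow-up is sound, except for outcomes never obtained and for opt-outs. If an opted-out baby stays in the case fatality denominator after a recorded death has been deleted, later follow-up cannot correct the ratio. This is a should-fix matter of interim reporting and not a flaw in the primary incidence estimates.

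**What to change.** Amend the paragraph on immediate analysis so that each interim report does the following:

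- Shows deaths over all confirmed cases, labelled provisional and a lower bound for the reported cases, with the number of unresolved outcomes.
- Shows the true upper bound beside it: deaths plus unresolved, over all confirmed cases.
- Adds case fatality restricted to cases with a fixed minimum follow-up. If the form records outcome or last-status dates, an Aalen-Johansen estimate of death against discharge alive, with a 95% confidence interval, could be used instead. The protocol lists date of death but does not mention a date of last status, so this needs checking against the data collection form first.
- Does not present deaths over deaths plus discharges as an upper figure.

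State that babies opted out with outcome deleted leave both numerator and denominator of case fatality but stay in incidence. Use plain deaths over cases as the definitive figure only once follow-up is complete.

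The cost is a short change of wording, one or two extra lines in each report, and wide bounds early on. Counting open cases needs no new data item, because still being admitted is already a recorded outcome and unknown outcomes are already flagged for re-contact.
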